 What was the calculated preoperative risk of anastomotic leak? Have there been unforeseen surgical events, operative field contamination or technical difficulties during the operation that will influence this risk? Does the patient have the physiological reserve to withstand the adverse effects of anastomotic leak? 		
Q3: What type of anastomosis is planned?		
Stapled Is the bowel being anastomosed healthy? Is the bowel oedematous and/or inflamed? Is there presence of pus?	Handsewn Is there any bowel end ischaemia? Is there luminal discrepancy? What anatomical arrangement is planned? (Side to side/end to side/end to end)	
Is there any bowel end ischaemia? Is there any mesenteric torsion? What instruments are required? What stapler size is required?	Which sutures are to be used? Interrupted or continuous One or two layers	

APPENDIX 2. EAGLE Case Report Form

Local Patient Identifier	not uploaded to REDO	Сар	Unique REDCap Identifier	
Pre-operative data				
Age (on day of operation) Years				
Sex		Male /	Female	
American Society of Anaest grade	thesiologists (ASA)	1/2/3	8/ 4/ 5	
Previous abdominal surgery	/	No / Ye	es	
History of ischemic heart discerebrovascular disease	sease or	No / Ye	es	
History of diabetes mellitus		No / Ye	es	
Body Mass Index >30		No / Ye	es	
Oral anti-coagulants		No / Ye	es	
Pre-operative total protein le	evel (g/dL)			
– nearest 0.5 units				
Pre-operative haemoglobin	(g/dL)			
Procedure indication		Malign	ancy / Inflammatory bowel disease / Other	
	Intra	a-operative	data	
Bowel preparation			Mechanical bowel preparation only / Mechanical preparation with oral antibiotics	I
Primary operating surgeon			tant colorectal surgeon / Trainee colorectal n / Consultant general surgeon / Trainee genera n	ıl
Most senior surgeon in theatre			tant colorectal surgeon / Trainee colorectal n / Consultant general surgeon / Trainee genera n	ıİ
Procedure urgency			e (planned) / Expedited (within two weeks of n to operate) / Emergency (unplanned)	
Operative approach			Laparoscopic (completion, conversion to open), c (completion, conversion to open)	
Operative field contamination	on	Clean-	contaminated / Contaminated / Dirty	
Anastomosis formed		Stapled / Handsewn / No anastomosis (end ileostomy formation)		
If yes: Anastomotic	If yes: Anastomotic configuration Side-to-side / end-to-end		-side / end-to-side / end-to-end	
If yes: Is there a defunctioning loop ileostomy No / Yes		es		
If yes: Was the ana	stomosis tested?	No / Ye	es -air leak test / Yes - probed with forceps	
If yes: Did the anas revision?	tomosis require	No / Ye	es	

Intraoperative complications	Blood loss >1L / Operating time >4h / Solid organ or ureteric injury / Vascular injury / Blood transfusion / Hemodynamic instability / Vasopressor requirement (select all that apply)
Duration of surgery (minutes)	4 00 / 04 440 / 400 470 / 400 000 / 040
knife-to-skin to completion of skin closure	1-60 / 61-119/ 120-179/ 180-239/ ≥240
Was an ESCP Safe-anastomosis Checklist completed?	Yes / No
Was anastomotic leak risk calculated pre-operatively ?	Yes / No
Was anastomotic leak risk calculated intra- operatively?	Yes / No
Has the senior surgeon completed the Safe- anastomosis module?	Yes / No
Pos	st-operative data
Post-operative critical care admission	None / Planned from theatre / Unplanned from theatre / Unplanned from ward
Total length of hospital stay	Days (up to 30 postoperative days)
Anastomotic leak or intra-abdominal/pelvic collection	None / Grade A – requiring no further intervention, radiologically diagnosed / Grade B – requiring radiological reintervention / Grade C – requiring surgical reintervention
If yes: How was the leak diagnosed?	Clinical diagnosis only/ Ultrasound imaging/ CT imaging/ MR imagining/ Intraoperative diagnosis
Re-operation within 30 days	No / Yes
Re-admission within 30 days	No / Yes
Mortality within 30 days	No / Yes

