The primary outcome measure is anastomotic leak within 30-days of surgery (with Day 0 as the day of surgery). The denominator for the primary outcome is the total for patients who had a primary anastomosis. The numerator is anastomotic leak, defined as a composite of either:

Anastomotic leakage identified radiologically or clinically

or

Intraperitoneal (abdominal or pelvic) fluid collection identified radiologically, as per the
 Centre for Disease Control Criteria for Organ Space infection

SECONDARY OUTCOME MEASURES

The denominator is the total for patients who had a primary anastomosis:

Reoperation for anastomotic leak, within 30-days

The denominator is the total for all patients:

- Reoperation for any cause, within 30-days
- Unplanned admission to critical care, within 30 days
- Readmission within 30 days.
- · Length of hospital stay, up to 30-days
- Mortality within 30-days.
- Rate of ileostomy without anastomosis.
- Rate of defunctioning ileostomy with anastomosis.

PROCESS EVALUATION

Adherence to the key components of the intervention will be recorded on the Anastomosis Checklist. This will be a printed sheet which is completed by a circulating staff member in theatre. Specifically they will record:

- Whether pre-operative risk stratification was performed.
- Whether intra-operative risk stratification was performed.
- Whether the surgeon participated in the Anastomosis Checklist.

This process will be co-ordinated by the Theatre Nurse co-Principal Investigator. At the end of the operation, the Anastomosis Checklist will be filed in the patient notes. This will subsequently be accessed by the data collection team to extract data to the CRF.

DATA COLLECTION AND FOLLOW-UP

Data will be collected in two phases. During the index admission pre-operative and intra-operative data will be collected. Local Principal Investigators will establish pathways in their hospitals to ensure robust data collection; for example, pre-operative data could be collected on the morning prior to surgery, with intra-operative data fields completed in theatre immediately following completion of the procedure. Alternatively all data could be collected in theatre, or in the post-operative ward.

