All patients, including those who did not have a primary anastomosis, will be followed-up to a maximum of 30-days postoperatively (with Day 0 being the day of surgery) by a review of their inpatient health records, routine clinic visit letters, and reports for postoperative radiological investigations arranged as part of normal patient care. There will be no additional patient contact (telephone or in-person) beyond what is normal clinical practice at each centre. The study is designed efficiently so that existing patient follow-up pathways and health records can be used, with only data that is routinely collected as part of normal clinical care being captured.

Most anastomotic leaks following ileocolic anastomosis occur in the early post-operative period (days 4-14). Although a small number of anastomotic leaks occur beyond day 30, limiting follow-up to 30 days will ensure that the vast majority of leaks are captured.

SAMPLE SIZE

Assuming no decay in the intracluster correlation over time, our 2015 data suggest an ICC of approximately 0.05 [REF 2017]. Based on feasibility (below), we assume that each hospital provides data on 10 patients over a 2-month recruitment period (5 per hospital per month). An overall 'design effect' or sample size inflation factor for our cluster-randomised dogleg design relative to an individually randomised parallel groups design can then be calculated. Using this design effect, to detect a 30% relative risk reduction in leak rate from 8.1 to 5.6% with 80% power at the 5% significance level requires 292 clusters and 3,895 patients. In practice there will be variation in recruitment at different hospitals, which can be expected to increase the required sample size. Following a published rule of thumb, we assume that this inflates the sample size by at most 14% leading to a required sample size of 333 clusters and 4,440 patients.

PROJECTED RECRUITMENT

Data for 3,208 right colectomies was submitted by 284 centres over a 2 month period to the 2015 ESCP Right Hemicolectomy Audit; an average of 11.3 patients per 2 months. 81% the sites recruited >10 patients over the 2-month period. A mean of 10 patients per centre is required for each 2 month recruitment period.

Patients per centre (2 months)	Proportion of centres
1-5	19% (n=53)
6-10	37% (n=104)

11-15	22% (n=63)
16-20	14% (n=39)
21-30	6% (n=17)
31+	3% (n=8)

Table 1: Patient recruitment data from 2015 ESCP Right Colectomy & Ileocaecal Resection Audit

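### The case report form's one critical-care item cannot hold both a planned admission from theatre and a later unplanned one, and no rule says which to enter, so events of a secondary outcome can be lost

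*Protocol*

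**What the plan says.** The section Secondary Outcome Measures lists "Unplanned admission to critical care, within 30 days" and introduces the group to which it belongs with "The denominator is the total for all patients". Patients who go to critical care by plan after surgery are therefore in the denominator and at risk of the event. Data Collection and Follow-up has every patient followed through health records to day 30, with surgery as day 0.

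The only field on critical care in Appendix 2 is labelled "Post-operative critical care admission", and its answers are "None / Planned from theatre / Unplanned from theatre / Unplanned from ward". No instruction accompanies it. On the same form, the item on intraoperative complications carries the instruction "select all that apply". Further down, reoperation, readmission ("Re-admission within 30 days") and mortality are separate No/Yes items that do not mention critical care.

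**The concern.** The item asks two questions at once. One is whether critical care was planned as part of the operation, which is a fact about the end of surgery. The other is whether the patient needed critical care unexpectedly at some point up to day 30, which is the outcome. The two can both be true of one patient: a planned stay, step-down to the ward, a leak, and a return to critical care.

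If such a patient is entered under the planned option, the outcome event disappears from the database. If the ward option is entered, the outcome is kept and the planned stay is lost. With no stated rule, the recorded rate depends partly on local habit. An analysis plan cannot repair this later, because it cannot restore an event that was not collected.

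**Working it through.** No alpha, power, rate or sample size enters here, and the protocol states no figure to reproduce. The check sets the outcome definition against the form and goes through the possible patient courses.

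**Step 1: is the item single choice?** The form does not say so in words. Two features of the layout point that way. The options are separated by slashes, as in ASA grade, procedure urgency and leak grade, each of which takes one answer. The item that does allow several answers is marked as such ("select all that apply"), and this one is not. Single choice is thus a strong inference from the printed form.

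**Step 2: what happens to each course under one answer?**

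| Course up to day 30 | Has the outcome? | What the form can record |
|---|---|---|
| No critical care | No | Correct |
| Planned stay only | No | Correct |
| Unplanned from theatre only | Yes | Correct |
| Unplanned from ward only | Yes | Correct |
| Unplanned from theatre, later unplanned from ward | Yes | Either answer keeps the outcome |
| Planned from theatre, later unplanned from ward | Yes | Planned option: event lost. Ward option: event kept, planned stay lost. No rule |
| Discharged, then readmitted from home directly to critical care | Yes | No option clearly fits |

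The problem is confined to the last two rows.

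**Step 3: does another field recover the event?** Reoperation, readmission and mortality are plain No/Yes items. The leak item grades the leak by the reintervention it required. Length of stay is a total number of days. None says whether the patient was in critical care.

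**Step 4: how large could the loss be?** Let p be the share of all patients with a planned admission from theatre, u the fraction of these who later have an unplanned admission, and c the fraction of that last group whom sites enter under the planned option. Then

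events lost, as a share of all patients = p × u × c.

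- If every site enters the ward option, c = 0 and the loss is 0.
- If every site enters the planned option, c = 1 and the loss is p × u, which is all events in this group.

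The protocol gives none of p, u or c, so the range cannot be narrowed. Any loss from direct readmissions to critical care would come on top and is equally unknown.

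**The case against.** The strongest reply is that the form does not make the event unrecordable. A reader might infer that a patient with a planned admission can never be counted as having the outcome. The protocol does not support that: nothing stops a site from entering the ward option for a patient who steps down and comes back, and the outcome is then kept. This part of the reply stands, and it is why the point concerns a missing rule and a possible under-count, not a certain loss.

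Second, the REDCap build and any completion guidance are not shown. Sites are trained on follow-up, and data staff check entries and raise queries. That may reduce inconsistency. However, a query can find only what looks wrong, and a planned admission entered for a patient who had one looks right.

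Third, a reader might infer a bias in favour of the intervention: calculating risk before surgery leads teams to book more planned beds, so fewer admissions are recorded as unplanned. The protocol does not support this. Its section Ethics & Consent says that usual care before and after surgery is not affected by the intervention. The checklist decision concerns anastomosis or stoma, and none of its questions is about booking critical care. The Blinding section does say that outcome assessors cannot be blinded, so an ambiguous entry is made with knowledge of the allocation, but that gives no direction.

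Fourth, the item's label has no 30-day window, which a reader might count as a further defect. It is not one of substance. The outcome definition and the follow-up section both set the window, Data Management has data collected at 30 days, and the leak item for the primary outcome has no window in its label either.

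**Conclusion.** The point holds in a limited form. Read as printed, the critical-care item cannot record both a planned admission from theatre and a later unplanned one. It gives no precedence rule, and it has no clear option for readmission from home directly to critical care. The outcome event is lost whenever the planned option is entered for a patient who had both, and coding may differ between sites.

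Among patients with both kinds of admission, the loss lies anywhere between none and all of their events. It cannot be sized further from the protocol, and no direction of bias between the intervention and control conditions is shown. The conclusion assumes that the item is single choice, which is inferred from the layout, and that no completion rule exists outside the document.

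One of the eight listed secondary outcomes is affected. The primary outcome, its analysis and the sample size are untouched. This is a cheap improvement in data capture for a named outcome, not a threat to the trial's main conclusion.

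**What to change.** Replace the single item with two:

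- (a) Planned critical-care admission directly from theatre: No / Yes.
- (b) Any unplanned critical-care admission within 30 days: No / Yes, and if yes, whether from theatre, from the ward (including after step-down from a planned stay) or on readmission.

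Define the secondary outcome as any Yes to (b).

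The cost is one extra field per patient and reworded options in REDCap. If the form cannot be restructured, a printed precedence rule (any unplanned admission up to day 30 takes priority over a planned one, and direct readmission to critical care counts as unplanned) would protect the outcome, at the price of losing the planned stay in patients who had both.

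The split leaves one thing unchanged. A patient who goes straight from theatre to critical care still counts as planned or unplanned according to whether a bed was booked. That follows from the outcome definition, not from the layout of the form.

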The study intervention will be introduced at a specific timepoint determined by the randomisation sequence. Sites will not be exposed to the study intervention before their allocated timing and this will be ensured by time-locked password access to QII materials.

Intervention details

The EAGLE Safe-anastomosis Quality Improvement Intervention (QII) is a behavioural change intervention composed of three parts:

1. Routine patient-level stratification of risk of anastomotic leak

Calculation of a preoperative risk for each patient undergoing right colectomy or ileocaecal resection using the anastomoticleak.com risk calculator. This includes six factors: Gender; Body Mass Index >30; Anticoagulant use; Intraoperative complication; Serum protein level; Hospital size. Investigators will be trained and encouraged to preoperatively calculate the risk with or without an intraoperative complication. This risk estimate will be used to inform shared decision

making with the patient preoperatively, and will be reviewed in light of intraoperative events as part of the ECSP Safe-anastomosis Checklist.

2. ESCP Safe-anastomosis Checklist

The ESCP Safe-anastomosis Checklist will be implemented in-theatre, immediately prior to the time of formation of an anastomosis or formation of a stoma; this can be before or after transection of the bowel. The checklist should be completed by an unscrubbed member of the theatre team in partnership with the operating surgeon(s), other members of the surgical team, the scrub nurse(s), anaesthetist(s) and operating department practitioner(s).

The Safe-anastomosis checklist (Appendix 1) consists of:

- (1) Review of any concerns from the anaesthetist, including the anaesthetic risk, haemodynamic instability, vasopressors, blood transfusion, operating time greater than 4 hours, or blood loss greater than 100mls;
- (2) Review of any concerns from the surgical team, including the surgeon, scrub staff and operating theatre practitioners. A consensus decision for primary anastomosis (with or without defunctioning enterostomy) or defunctioning enterostomy without anastomosis will be then made by the operating surgeon.
- (3) If the consensus decision is to proceed with anastomosis; planning equipment, anastomotic configuration, and delivery of an agreed anastomotic technique, including intra-operative checking of anastomosis integrity.

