STATISTICAL ANALYSIS PLAN

This will be conducted on an intention-to-treat basis i.e. all patients recorded in the database during the scheduled 2-month recruitment periods will be included, and those in the second period will be considered exposed to the intervention regardless of whether learning from the intervention was actually implemented. The primary outcome will be 30-day anastomotic leak rate. In the primary analysis, 30-day leak rate will be modelled using mixed effects logistic regression with random cluster (hospital) effects allowing inclusion of baseline risk factors such as co-morbid disease and ASA score and adjustment for a fixed time effect between time periods.

Planned additional analyses

Pre-planned exploratory sub-group analyses of the primary outcome will be performed in the following groups:

At cluster (hospital) level:

- Number of beds (<500 versus ≥500 total hospital beds).
- Right colectomy volume (<10 patients versus ≥10 patients per 2 month period).
- Early adoption (early versus late study entrants).
- Health service expenditure per capita in purchasing parity (top versus middle versus bottom tertile).
- Proportion of operating surgeons in each centre completing the online training modules prior to 'post-implementation' data collection (high [≥80%], intermediate [50-79%], low [<50%]).
- World Bank income group (high versus middle/low income country).

At patient level:

- Indication for surgery (malignant versus benign, e.g. inflammatory bowel disease).
- Procedure urgency (elective versus expedited/ emergency).
- Age (≤65 years versus >65 years).
- Operative approach (open versus laparoscopic/ robotic).
- Anastomotic technique (stapled versus handsewn anastomosis).
- Primary operating surgeon experience as reported (trainee versus consultant).
- Primary operating surgeon specialism as reported (general versus colorectal surgeon).

Reverse analysis will also be undertaken to explore what are the characteristics of hospitals with a big change versus no change, and do these differ in respect of cluster characteristics.

DATA HANDLING AND RECORD KEEPING

Source Data

Source data within the EAGLE study will be kept as part of the participants' medical notes generated and maintained at site. As all data collected and analysed within the EAGLE study are routinely collected, source data will only be within the medical notes.

Data Management

Information will be collected at the following times:

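### The case report form has no answer for a leak diagnosed clinically and managed without reintervention, although the primary outcome counts it

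*Protocol*

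**What the plan says.** **Outcome definition.** Protocol, Primary Outcome Measure, gives a composite of two components. The first is "Anastomotic leakage identified radiologically or clinically". The second is an intraperitoneal "fluid collection identified radiologically, as per the" CDC organ-space criteria. Only the second is limited to imaging, and neither requires reintervention.

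**Form.** In Appendix 2, Post-operative data, one item records leak or collection. Its answers are none, Grade A ("requiring no further intervention, radiologically diagnosed"), Grade B ("requiring radiological reintervention") and Grade C ("requiring surgical reintervention"). A follow-up item, opened only when a leak has been entered, asks how it was diagnosed and accepts a purely clinical diagnosis. The mortality item is yes/no, without cause.

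**Assessment.** The Blinding section states that neither surgeon nor outcome assessor can be blinded. It relies instead on an objective endpoint and standardised data collection.

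**Inclusion and period.** The Statistical Analysis Plan section of the protocol says that "all patients recorded in the database during the scheduled 2-month recruitment periods will be included". It treats second-period patients as exposed and adjusts for a fixed time effect. The printed form has no operation date or period field.

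**Blood loss.** The checklist (ESCP Safe-anastomosis Checklist section and the printed checklist) prompts on "blood loss greater than 100mls". The form's list of intraoperative complications has "Blood loss >1L".

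**The concern.** The form is the only described route by which a primary event reaches the analysis. If the definition admits a class of leak that the form cannot express, whether those leaks are counted depends on how each site improvises. Staff who know whether the intervention has been introduced make that decision, and no printed rule guides them. Some events may be lost. If the habit changes between conditions, part of the estimated effect would reflect coding. This also weakens the safeguard that the Blinding section offers in place of blinded assessment.

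A related weakness is that inclusion is worded by when a patient was recorded, while exposure depends on when the operation took place. Patient Identification allows patients to be found after surgery, and Patient Entry assigns the REDCap identifier on upload, so the two times can differ.

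**Working it through.** **1. Definition against form.** Cross diagnosis with management for the leak component:

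| Diagnosis | No reintervention | Radiological reintervention | Surgical reintervention |
|---|---|---|---|
| Radiological | Grade A | Grade B | Grade C |
| Clinical only | no valid answer | Grade B | Grade C |

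All six cells meet the outcome definition; five have a valid code. Clinically diagnosed leaks are therefore recordable when they lead to reintervention, and the gap is one cell. A death before reintervention falls in the same cell. To reach the follow-up item that accepts a clinical diagnosis, the site must already have chosen a grade. The available entries are none (event lost) or, most naturally, Grade A (event kept, mislabelled).

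**2. Reproducing the planned size.** Inputs from the Sample Size section: 8.1% v 5.6%, 80% power, 5% significance (taken as two-sided), ICC 0.05 without decay, 10 patients per hospital-period, 14% inflation.

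- Individually randomised, per arm: n = [1.96√(2 × 0.0685 × 0.9315) + 0.842√(0.081 × 0.919 + 0.056 × 0.944)]² / 0.025² = 1,602, so 3,204 in total.
- Variance of a hospital-period mean, in units of the individual variance: 0.05 + 0.95/10 = 0.145. Covariance of the two periods in a sequence 2 hospital: 0.05.
- Per triplet, the effect is the average of two within-period differences. Its variance is [0.145 + 0.145 + 2(0.145 − 0.05)]/4 = 0.12. For 40 individually randomised patients it is 4/40 = 0.10. Design effect = 1.20.
- 3,204 × 1.20 = 3,845 patients; 3,845 × 3/40 = 288 clusters. The plan has 3,895 and 292, which is within about 1.3%.
- 292 × 1.14 = 332.9 and 3,895 × 1.14 = 4,440.3, matching 333 and 4,440.

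The plan's figure is not in dispute; it serves as the 80% reference.

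**3. Equal loss.** If a fraction f of leaks goes unrecorded in both conditions, both rates are multiplied by (1 − f). With 1,602 per arm:

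| f (assumed) | Rates | Power |
|---|---|---|
| 0 | 8.10% v 5.60% | 80.0% |
| 2% | 7.94% v 5.49% | 79.2% |
| 5% | 7.70% v 5.32% | 77.8% |
| 10% | 7.29% v 5.04% | 75.4% |
| 20% | 6.48% v 4.48% | 70.1% |

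The risk ratio stays at 5.6/8.1 = 0.69.

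**4. Unequal loss (illustration, 5% in one condition only).**

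- Lost only after the intervention: 5.6 × 0.95 = 5.32%, and 5.32/8.1 = 0.66.
- Lost only before it: 8.1 × 0.95 = 7.695%, and 5.6/7.695 = 0.73.
- With no true effect, loss only after the intervention would show a risk ratio of 0.95.

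**5. Where period matters.** Study Design has sequence 1 collecting data only after the intervention and sequence 3 only before it. Allocation therefore fixes exposure for both. Sequence 2 supplies 2 of the 4 hospital-periods in each triplet: 20/40 = 50% of planned patients. Only there is a date or period marker needed to assign exposure.

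**6. Blood loss.** 1,000 mL / 100 mL = 10. The item enters neither the primary outcome nor the exposure definition.

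**The case against.** **On the leak item.** The outcome is binary, and the follow-up item shows that the form's authors expected clinically diagnosed leaks to be entered. A site that chooses Grade A and then marks the diagnosis as clinical still contributes an event; only the grade is wrong. A reader might infer that these events are simply lost. The documents do not support that: loss occurs only where a site enters none, and nothing says how often it would. The table in step 3 is therefore a worst case for each assumed f. It also takes the plan's 80% as given, although the outcome's denominator is restricted to patients with a primary anastomosis. What stands is that the form has no truthful answer for a defined primary event and no rule for choosing between untrue ones.

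**On period.** A reader might infer that exposure period cannot be derived or checked at all. That goes too far.

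- Allocation settles exposure in sequences 1 and 3.
- Data validation ties eligible cases to surgery within the centre's data collection window.
- Sites keep the link between study number and patient, and theatre logbooks are reviewed in 10% of centres.
- The printed form also lacks a hospital identifier, although hospital is the random effect, so it is evidently not the full set of REDCap fields.
- In sequence 2, entry would have to lag beyond the one-month implementation gap to cross from one condition to the other.

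What stands is the wording of the inclusion rule and the absence of any stated operation-date field.

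**On blood loss.** A reader might link the mismatch to the primary outcome or to the adherence audit. Neither link holds. The Process Evaluation lists three adherence items, and blood loss is not among them.

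**Conclusion.** The concern holds for the leak item. The protocol's definition and its form contradict each other for one class of primary event, and unblinded staff are left to resolve it. The size is unknown because the documents give no share for such leaks. Under an assumed 2% to 10%, all entered as none and equally in both conditions, power falls from 80% to between about 79% and 75%. The more serious possibility is a coding habit that differs between conditions, which would bias the estimate in either direction.

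The period point holds only as a matter of wording and confirmation. Inclusion and period should rest on the operation, and this bears on about half of planned patients. The blood-loss discrepancy is real, separate and minor, and does not affect the derivation of primary events or period.

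**What to change.** 1. Add a response option to the leak item for a leak diagnosed clinically without radiological or surgical reintervention, stating that it includes death before reintervention. Alternatively, ask leak yes/no first and grade second. Either way, every leak meeting the Primary Outcome Measure definition must be recordable.
2. In the Statistical Analysis Plan section, define inclusion and period by date of operation, or by study week where dates raise privacy concerns, instead of by recording in the database. Confirm that the eCRF captures it.
3. Separately, reconcile the blood-loss threshold in the checklist section and the printed checklist with the one in Appendix 2. No view is taken here on which is right.

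The cost is a small REDCap and form revision, a short note to sites and one reworded sentence. Sample size and analysis model are unaffected.
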